## 10 SAFETY MANAGEMENT

To assure that the study meets expectations and any risk to participants is reduced to a minimum, the proposed study will use the Executive Committee and Safety Monitoring Committee (SMC) that was created in the parent study (Connect-Home Clinical Trial [R01NR017636]).

Executive Committee. The Executive Committee of the parent study will oversee the conduct of the study. The PI will chair the committee, which will meet quarterly, or more often as warranted, to review the activities of the study including management, personnel, recruitment, performance, and any emerging problems.

Safety Monitoring Committee (SMC). The SMC has seven members. The members of the Executive Committee and two members of the committee who will be independent of the protocol. Despite usual precautions, we are aware that adverse events may occur and this committee will monitor the occurrence of adverse events and the overall risk of the study to SNF patients, caregivers and staff. We will develop a system to test whether abnormalities are equally distributed between the intervention and control groups. Data will be presented to the committee if a significant increase in abnormalities is noted. The SMC will use the following stopping rules: (1) the intervention is associated with adverse effects that significantly impact the risk-benefit ratio, (2) study recruitment or retention becomes futile, (3) any new information becomes available during the trial that necessitates stopping the trial; or (4) other situations occur that might warrant stopping the trial. They will use these standards before they recommend modification or premature termination of the study on the basis of safety. Additionally, standards for discontinuing subjects from the study due to related adverse events will be established. The SMC will provide the PI with recommendations regarding problems that would require premature termination of the study for safety reasons. Minutes of each meeting will be kept, and all actions and decisions documented to establish an audit trail. The committee will also provide the PI with advice on whether there is any reason to change the design of the study.

Any serious adverse events or deaths that occur during the study will be reported by telephone immediately to the Human Participants Research Review Committee Chairperson. An incident report will be sent by electronic mail by the Executive Committee members and the project manager. The PI will follow-up immediately with patient or caregiver to investigate, and prepare a report for all members of the Human Participants Committee, and comply with all regulations regarding the reporting of serious adverse events. The event will be evaluated for relatedness to the study intervention. The PI or a Co-Investigator in his absence will be responsible for complying with all regulations concerning the reporting of a serious adverse event and will prepare a full report for NIH if the event is related to study intervention. The PI will meet with the Co-Investigators and project manager and make a subject or study termination decision as the situation warrants. Process notes will be kept concerning any termination decisions.

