Connect-Home Plus is a two-step transitional care intervention: 1) SNF staff create an individualized Transition Plan or Care and prepare the patient with ADRD and caregiver to manage the patient's illness at home; and 2) within 3 days of discharge a home care nurse visits the patient and caregiver at home and within 30 days of SNF discharge, a dementia caregiving specialist calls the caregiver three times at home and helps them implement the written Transition Plan of Care. Both intervention steps focus on 6 key care needs to optimize patient and caregiver outcomes: 1) home safety and level of assistance; 2) advance care planning; 3) symptom management; 4) medication reconciliation; 5) function. See **Section 5** for additional detail.

c. Follow- up procedures (by visits)

Schedule of Activities for Patients:

See next page

Assessments and Procedures	Screen	Pre Discharge	Discharge	1-3 days post discharge	7 Days Post-Discharge (+ 10/- 3 days)	21 Days Post-Discharge (+/- 7 days)	30 Days Post-Discharge (+/- 7 days)
Informed Consent	X						
Confirm Eligibility	X						
Baseline interview		X					
Chart Abstraction					X		
Connect-Home in SNF		X					
Home Care Nurse visits				X			
CTM-15					X		
Satisfaction interview						X	
DEMQoL							X
Life Space Assessment							X
Chart Abstraction							X
Hospital and ED use assessment							X

Schedule of Activities for Caregivers:

Assessments and Procedures	Screen	Pre Discharge	Discharge	1-3 days post discharge	7 Days Post-Discharge (+ 10/- 3 days)	21 Days Post-Discharge (+/- 7 days)	30 Days Post-Discharge (+/- 7 days)
Informed Consent	X						
Confirm Eligibility	X						
Baseline interview		X					
Connect-Home in SNF		X					
Home Care Nurse visits				X			
Readiness for Caregiving assessment					X		
Dementia Caregiving Specialist calls				X	X	X	
Satisfaction interview						X	
DEMQoL-proxy assessment							X
Caregiver burden and distress assessment							X

d. Subject Completion/ Withdrawal procedures

All identifying information will be destroyed at the earliest possible time following completion of the study. In addition, data will be reported in aggregate form, without identifying information by site or individual. Publications arising from the study will not contain personal information.

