#### Variables that will be abstracted from the intervention log maintained by the dementia caregiving specialist (study staff)

As part of Connect-Home Plus, a dementia caregiver specialist will maintain a written log of details from supportive calls with the caregiver after the patient transfer from SNF to home, including one post-discharge support call within 72 hours after discharge and two additional calls within one month of discharge. Data collected from the Call-back log will include: number of days after discharge on which the call occurred, duration of the call, transition challenges identified on the call, caregiver education provided on the call, and follow-up actions and next steps identified on the call.

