- Dementia Quality of Life-Proxy measure (DEMQOL-Proxy). When the patient is unable to rate their quality of life, the quality of life will be rated by their caregiver, using the Dementia Quality of Life-Proxy measure.(33) The score range is 31-124 with higher scores indicating better quality of life.
- Self-Reported Days of ED or Hospital Use 30 Days After Skilled Nursing Facility Discharge. Patient's days of acute care use will be measured using the self-reported number of combined number of days the patients pends in the Emergency Department (ED) or hospital in 30 days after SNF discharge.(19)
- Zarit Caregiver Burden Scale. Caregiver burden will be measured using the Zarit Caregiver Burden Scale, which includes 12 items on a five-point scale, measuring caregiver perceptions that "caregiving has an adverse effect on their emotional, social, financial, physical and spiritual functioning."(34) Scores range 0-48; higher scores are associated with depression and social isolation.
- Distress Thermometer. Caregiver distress will be measured using the Distress Thermometer, which includes 1 item on an 11-point scale, measuring negative affect (e.g., sadness and fear) related to caregiving for a severely ill person. Score ranges 0-10, with scores >4 associated with poor coping and depression.(35)

a. Safety Evaluations

- Study progress and safety will be reviewed monthly (and more frequently if needed). Progress reports will include patient and caregiver recruitment, retention/attrition, and adverse events. In addition, safety evaluation will include (1) whether adverse event rates are consistent with pre-study assumptions; (2) reason for dropouts from the study; (3) whether all participants met entry criteria; (4) whether continuation of the study is justified on the basis that additional data are needed to accomplish the stated aims of the study; and (5) conditions whereby the study might be terminated prematurely.
- An adverse event (AE) is any untoward medical occurrence in a subject temporally associated with participation in the clinical study or with use of the experimental agent being studied. An adverse finding can include a sign, symptom, abnormal assessment or any combination of these. A Serious Adverse Event (SAE) is any adverse event that results in one or more of the following outcomes:
  - Death
  - A life-threatening event
  - Inpatient hospitalization
  - A persistent or significant disability/incapacity

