  - Important medical event based upon appropriate medical judgment

Potential sources of information for identification of AEs include (but may not be limited to) nursing home staff reports of events while the patient is in the nursing home, and patient or caregiver reports of events while the patient is in the nursing home or at home. For example, the proposed study team will be in contact with the patient and caregiver over 30 days after the patient discharges from the nursing home to home. We will be calling the patient and caregiver at 7, 21 and 30 days. Any event that is discovered will be immediately relayed to the PI, or if he is away, another member of the research team so that we can execute safety plans and reporting plans described here.

AEs will be labeled according to severity, which is based on their impact on the patient. An AE will be termed 'mild' if it does not have an impact on the patient, 'moderate' if it causes the patient some minor inconvenience

and ‘severe’ if it causes a substantial disruption to the patient’s well-being. AEs will be categorized according to the likelihood that they are related to the study intervention. Specifically, they will be labeled either definitely, probably, possibly or unrelated to the study intervention. If any IRB actions occur, the PI will email a report within 24 hours for the Independent Monitor, the second Independent monitor, and the Program Officer in the NINR in accordance with requirements.

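### Hospitalisation is an SAE for immediate reporting, but the schedule asks about hospital use only at day 30, so earlier detection rests on spontaneous report

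*Combined protocol and SAP*

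**What the plan says.** Section 7 (Safety Evaluations) lists "Inpatient hospitalization" among the outcomes that make an adverse event serious, with no exemption for expected or unrelated admissions. Section 10 then says: "Any serious adverse events or deaths that occur during the study will be reported by telephone immediately".

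For finding events, Section 7 names reports from nursing home staff, patients and caregivers, and gives the study calls as its example: "We will be calling the patient and caregiver at 7, 21 and 30 days". Anything discovered is to be passed to the principal investigator (PI) at once.

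In the patient schedule (Section 6c), the row "Hospital and ED use assessment" has one mark, in the day-30 column, whose window is plus or minus 7 days. Day 7 carries the CTM-15 for patients and the readiness measure for caregivers. Day 21 carries the satisfaction interview for both. The caregiver schedule has no hospital or ED row.

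The dementia caregiving specialist, who is study staff, also phones the caregiver within 72 hours and twice more within a month. The items abstracted from that log (Section 7) include "duration of the call, transition challenges identified on the call, caregiver education provided on the call", together with call timing and follow-up actions. Hospital or ED use is not listed.

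**The concern.** The plan sets an immediate reporting duty for an event that it expects to be common, and names the calls as the means of finding it. It does not say that anyone will ask about admissions on the first two calls. Chart abstraction does not clearly fill the gap, because Section 7 describes it as drawn from the SNF record and not as covering admissions after discharge.

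Two things are at stake. SAEs may reach the PI and the Safety Monitoring Committee later than the reporting rule implies. The secondary outcome, days of ED or hospital use in 30 days, also depends on one recall over the whole period, in a sample selected for cognitive impairment or answered for by a caregiver.

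**Working it through.** The plan gives no figure for detection delay, so there is none to reproduce.

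**Inputs**
- 20 patients (Section 5c).
- Background 30-day rehospitalisation of 23% in persons with ADRD (Section 3, Relevant Literature and Data). Applying it to this pilot is an assumption.
- Call windows from Section 6c: day 4 to 17, day 14 to 28, and day 23 to 37.
- Timing of admissions within 30 days is not given. Base assumption: uniform. Alternative: front-loaded (exponential with mean 10 days, truncated at day 30).

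**Expected number of patients**
- Rehospitalised within 30 days: 20 × 0.23 = 4.6.
- Chance of at least one: 1 − 0.77^20 = 0.995.
- Before day 21, uniform timing: 4.6 × 21/30 = 3.2. At assumed rates of 10% and 30%, 20 × rate × 21/30 gives 1.4 and 4.2.
- These count admissions that occur before day 21, not admissions that are missed.

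**Mean delay from admission to detection, uniform timing**

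For calls on set days, the mean is the sum of (gap squared)/2 over the gaps, divided by 30.
- Only the day-30 question reveals admissions: 30²/(2 × 30) = 15 days, with 53% of delays (16/30) above 14 days.
- Same, but asked on day 37: 15 + 7 = 22 days.
- Every call at days 7, 21 and 30 reveals admissions: (7² + 14² + 9²)/(2 × 30) = 326/60 = 5.4 days, maximum 14 days.
- Adding a revealing specialist call at day 3 changes 5.4 to 5.0 days.

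The current plan lies somewhere between 5.4 and 15 days, depending on how often admissions are volunteered. The gain from asking is therefore between 0 and 15 − 5.4 = 9.6 days.

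**Sensitivity**
- Front-loaded timing: 21.6 days (day-30 question only) against 5.8 days (every call), so the upper end of the gain rises to about 15.7 days (21.57 − 5.84).
- Every call reveals admissions but all are at the late edge of their windows (days 17, 28, 37): mean 7.4 days, maximum 17, uniform timing.
- Widest gap that the windows allow (days 4, 28, 37): mean 10.4 days, maximum 24, uniform timing.

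**The outcome count**

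A day-30 call made on day 23 is within window but cannot see days 24 to 30, which is 7 of the 30 days in the outcome definition.

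**The case against.** A reader might infer that most hospitalisations will go undetected for weeks and that the immediate-reporting rule cannot work. The documents do not support that. The day-30 row serves a secondary outcome. Identification of adverse events is described separately and uses all three calls, with immediate relay of whatever is discovered. Read that way, reporting runs from discovery and the two sections are compatible. The specialist's calls record transition challenges, and the day-21 interview covers managing at home and unmet needs. A patient who is in hospital when a call is made would probably be noticed. Most delays lasting weeks would follow only if every earlier contact missed the admission.

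Nor can it be shown that the specialist's form has no place for an admission. Section 7 lists what is abstracted from the log, not the whole form. Table 4 mentions a call-back script that is not reproduced. The consent form, where families might be told to notify the team, is not in the text available.

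The effect on oversight should not be overstated either. Twenty dyads over the 12 months in Section 8 is about 0.8 dyads per 15 days (about 1.7 if the study lasts the 6 months in the Synopsis). Safety review is monthly, so a delay of days will often leave a committee decision unchanged. The outcome is only described, not tested, and the caregiver may answer when the patient cannot.

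All of this limits the size of the problem. It does not remove it: no text says that anyone asks about admissions before day 30.

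**Conclusion.** The concern holds in a limited form. The reporting duty depends on discovery, and before the day-30 contact the visible plan leaves discovery to spontaneous report. The range of 5.4 to 15 days runs from complete to no detection at the earlier calls, so 9.6 days is a ceiling on the gain and not its expected value. It assumes uniform timing, calls on their nominal days, and a truthful answer whenever the question is put. The true position within the range cannot be found from the documents.

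The weakness in the outcome is more certain: one recall of about 30 days, cut short if the last call comes early. The change is worth making because it is cheap and serves both safety reporting and the outcome. It does not call the pilot's design into question.

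**What to change.** - In both schedules in Section 6c, add the existing hospital and ED question to the day-7 and day-21 calls, worded as since the last contact and with dates. Put it to the caregiver, and to the patient where able.
- Add a yes/no hospital or ED line to the specialist's call log if the form lacks one, with relay to the PI the same day.
- Build the 30-day count from dated episodes, counting each calendar day once across informants, so that overlapping reports are not summed twice.
- Ask the final question on or after day 30, so that the whole period is covered.
- State in Section 10 that immediate reporting runs from the time the study team becomes aware of the event.

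The cost is one short question at two calls already planned and at most one log line, with no new contact or staff. Calls become slightly longer, and the recorded SAE count will probably rise, which should be read as better ascertainment. The windows still permit a gap of up to 24 days between calls, so the change shortens delay without removing it.

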### Data and Safety Management

#### Study Identification Information

- NIH Study Number – TBD
- Study Title – Adapting Connect-Home Transitional Care to Fit the Unique Needs of Persons with Cognitive Impairment and their Caregivers: A Pilot Study

- Name of Principal Investigator – [name], RN

## Study Overview

Brief Description of the Purpose of the Study – The objectives of the proposed formative study are to adapt the Connect-Home transitional care intervention to fit the needs of persons with ADRD and their caregivers and to test the feasibility and acceptability of the adapted intervention in a total sample of 20 patients and 20 caregivers in two SNFs.

Adherence Statement – The Data Safety Monitoring Plan (DSMP) outlined below for the proposed study will adhere to the protocol approved by The University of North Carolina at Chapel Hill Office of Human Research and Ethics Institutional Review Board.

## Confidentiality

Protection of Subject Privacy – Protections of subject privacy in the proposed study are described in the following. In study activities related to Aim 1 and Aim 2, after enrollment we will collect baseline data from persons with ADRD in person while they are in the SNF (using surveys and a chart review) and baseline data from the caregiver in person or by telephone (using surveys). In study activities related to Aim 1, we will collect data from persons with ADRD and their caregivers within 14 days after discharge from the SNF to home. In study activities related to Aim 2, we will collect data from persons with ADRD and caregivers by telephone at Time 1 (seven days after SNF discharge), Time 2 (21 days after SNF discharge), and Time 3 (30 days after SNF discharge). In study activities related to Aim 1, we will also collect data from staff members in the SNF and home care agency. Data collected from staff will not include protected health information and will focus on the nature of transitional care and discharge planning provided for persons with ADRD and their caregivers. Appropriate questionnaires and measurements will be collected at all time points. All of the materials collected are for research purposes only, and data will be kept in strict confidence. No information will be given to anyone without permission from the subject. The consent form includes the informed consent statement required by The University of North Carolina at Chapel Hill. This statement guarantees confidentiality and identifies the subject as the owner of the information from the analysis. Confidentiality is assured by use of identification codes. All data will be identified with an identification code unique to the subject.

Database Protection –The database is secured with password protection. The data base includes ONLY coded information, and data are entered into the database under those identification numbers. Electronic communication with outside collaborators involves only unidentifiable information. The study database will comply with current data security standards, and will provide real-time data entry validation, and will provide audit trails documenting any changes or corrections of the study data. Data entry or review will require logging into a secure portal with a username and password. The database is hosted by the School of Nursing at the University of North Carolina-Chapel Hill, and is HIPAA-compliant. The two servers in the University of North Carolina School of Nursing are connected using a Compaq Storage Area Network (SAN), which has 728 gigabytes of shared storage, also deployed in a RAID 5 array, with an additional 72.8 gigabyte drive available as a spare that can be swapped into operation with no interruption of service. The servers are fully redundant; all services can run on either node or be load-balanced between them. The SONBACKUP, which operates exclusively to perform backup for our servers and personal computers. Backup is performed regularly on an HP Storage Works Super DLT 320 tape backup unit.

Explicit identifying information will be recorded on separate forms and will NOT be sent to the database; these forms will be maintained in a secure location.

Confidentiality During Adverse Event (AE) Reporting – AE reports and annual summaries will not include subject- identifiable material. Each will include the identification code only.

## 11. RECRUITMENT STRATEGY

The study team will use a limited waiver of HIPAA authorization to pre-screening for patient and caregiver eligibility during the SNF admission. The study team will recruit SNF patients and their caregivers in-person (or, when risk mitigation related to COVID-19 prevents in-person contact, we will recruit virtually, using an iPad and connection via ZOOM) within 10 days of their admission and will review the patient's medical record to confirm eligibility. For persons with ADRD, inclusion criteria are: (1) be able to speak English; (2) have a goal of discharge to home; (3) have a diagnosis of ADRD, or a BIMS score <13, or (for persons unable to complete the BIMS assessment) a CPS of  $\geq 3$  (calculated using data in the Minimum Data Set 3.0 and an algorithm for estimating cognitive impairment using Minimum Data Set MDS data other than BIMS (26, 27)); and (4) have a caregiver willing to participate. We will recruit a representative for persons with ADRD who have a legally authorized representative (LAR); in addition, we will recruit a family caregiver to represent persons admitted to the SNF who are not able to complete the BIMS or who have a BIMS score  $\leq 7$ . Exclusion criterion for patients: planned hospital readmission for procedures/treatments in next 30 days (thus distorting assessment of patient and caregiver outcomes). Inclusion criteria for caregivers: 1) self-reports assisting the patient at home; and 2) the ability to speak English. We will identify caregivers using documentation in the medical record that the caregiver provides care at home and/or is legally authorized representative of the person with ADRD. We will use procedures from the Connect-Home parent study to recruit staff, persons with ADRD, and caregivers. To recruit persons with ADRD and caregivers, a Research Coordinator (RC) will use a HIPAA waiver allowing prescreening for eligibility and will: 1) consult the nursing director in each SNF to identify persons admitted to the SNF; and 2) screen the medical record of persons with ADRD who are expected to be discharged home. Using IRB approved forms and consent procedures, the RC will recruit persons with ADRD and caregivers in-person or by phone during the SNF stay until the recruitment goal is reached. The RC will recruit staff using procedures from the parent study. All participants will give written informed consent for study participation.

